8.1 Demographics

The demographics age (35-39/40-45/46-50/51-55/56-60/>60years), gender (male/female), marital status (single.married/divorced/widowed), education level (illiterate/read & write/primary/preparatory/secondary/university), employment status (full time/part time/per diem/unemployed/retired/housewife), and occupation (no work/unskilled worker/manual skilled worker/managerial work/semi-professional(clerk)/professional) will be presented by number and percentage. Exploratory p-values of the Chi-Square test between treatment groups will be displayed.

8.2 Baseline Characteristics

The following variables will be included:

8.2.1 *Psychosocial scores*

Depressive symptoms using the BDI Scoring will be presented by appropriate descriptive statistics (mean, standard deviation, median, and interquartile range (IQA)). Exploratory p-values of the t-test between treatment groups will be calculated.

8.2.2 *Anthropometric measurements*

Anthropometric measurements including weight [kg], height [cm], BMI [kg/cm²], and waist circumference [cm] will be presented by appropriate descriptive statistics (mean, standard deviation, median, and interquartile range (IQA)). Exploratory p-values of the t-test between treatment groups will be calculated.

8.2.3 *Laboratory tests*

Laboratory tests including FPG [mg/dl], 2h PG [mg/dl], & HbA1c [%] will be presented by appropriate descriptive statistics (mean, standard deviation, median, and interquartile range (IQA)). Exploratory p-values of the t-test between treatment groups will be calculated.

8.2.4 *Medical Data*

The medical history of DM including age of onset [years], duration of DM [years], & family history of DM (non/father/mother/brothers/sisters/uncles/aunts) will be identified. The number of comorbidities and diabetes side effects will be recorded. The type of comorbidities (hypertension/dyslipidemia/gout/heart disease/others) and the type of diabetes side effects (neuropathy/nephropathy/retinopathy) will be identified. Medical data will be summarized by the appropriate descriptive statistics no, percentage, mean, standard deviation, median, interquartile range (IQA), minimum, and maximum.

8.2.5 Habits and lifestyle

The frequency of blood monitoring (every day/every week/once a month/every other month/few times a year); the mechanism of blood glucose monitoring (home/clinical laboratory); frequency of visiting doctor for follow up (twice a month/every month/every other month/few times a year); diet control (yes/no/sometimes); carbohydrates craving (always/many times/sometimes/never); the pattern of physical activity (yes/no/sometimes) will be identified. The data will be presented by number and percentage. Exploratory p-values of the Chi-Square test between treatment groups will be displayed.

8.2.6 Adherence to treatment

Type of diabetes medication (table/insulin); assessment for adherence based on MTA scale (%); and reasons for non-adherence (ineffective/side effects/forgetful/expensive/better without treatment) will be recorded. Adherence data will be presented by appropriate descriptive statistics (mean, standard deviation, median, and interquartile range (IQA). Exploratory p-values of the t-test and chi-square between treatment groups will be calculated.

The number of study CBT sessions and visited attended by the study groups will be recorded and presented as number and percentage.

9 Statistical Analysis

The analysis will be conducted according to the Consolidated Standards of Reporting Trials guideline (CONSORT). An academic statistician blinded to study groups conducted the study statistical analysis. Quantitative data will be examined for normality distribution using the Shapiro-Wilk's test ($p>0.05$) (Shapiro & Wilk 1965; Razali & Bee Wah 2011) test. Results of $p<0.05$ will be considered significant indicating non-normal distribution. A parametric Levene's test will be used to verify the equality of variances in the samples (homogeneity of variance) ($p>0.05$) (Nordstokke, & Zumbo 2010; Nordstokke et al. 2011).

Simple frequency distribution tables to provide a description for both groups will be generated. Quantitative variables will be summarized using. mean and standard deviation (SD) for normally distributed quantitative variables and median and interquartile ranges (IQR) for not normally distributed quantitative variables. While the number and percentage will be used to summarize qualitative variables.

Exploratory p-values of the student two-tailed independent t-test and Chi-Square test between study groups will be used for baseline quantitative and qualitative variables, respectively. P-values will be reported to three decimal places with p-values less than 0.001 reported as $p < 0.001$. We used 2-sided p-values with alpha ≤ 0.05 level of significance.

Two sets of analyses will be conducted corresponding to the study outcomes' endpoints: 1) the CBT group demonstrated improvement of HbA1c level at the end of the sessions and 2) the CBT group demonstrated improvement of depression score on BDI versus the control group.

9.1 Software

Pre coded data will be entered on Microsoft office excel program for windows, 2010. Data will be transferred to the Statistical Package for Social Science Version 21 (SPSS-V 21).

9.2 Analysis of Outcomes

9.2.1 primary analysis

The primary variable is the Hb A1c plasma level.

The primary endpoint is the difference between Hb A1c level at baseline and three months later.

The primary outcome is the change of Hb A1c, compared between the different treatment groups using an Analysis of Covariance (ANCOVA), the General Linear Modeling approach to compare the study groups. The HbA1c and BDI at baseline will serve as control variables. HbA1c and BDI values at baseline are the values obtained at

the first visit before the start of the intervention. If the HbA1c value at baseline is missing, the first HbA1c value obtained during the first subsequent visits will be used.

The following hypothesis will be tested:

$H_0: \mu_{CBT} = \mu_{control}$ versus $H_1: \mu_{CBT} \neq \mu_{control}$

Where μ_{CBT} and $\mu_{control}$ are the expected mean values of the differences in HbA1c values belonging to the CBT and the control groups. The hypothesis will be tested on a 2-sided p-value with alpha ≤ 0.05 level of significance. The results will be displayed by means of the p-value, standard deviation of unadjusted values, and 95%-confidence interval. For that, the assumption of homogeneity of regression slope will be examined by testing the interaction effect of the independent variable and the covariate.

The secondary variable is the BDI score.

The secondary endpoint is the difference between BDI at baseline and three months later.

The secondary outcome is the change of BDI compared between the different study groups using an Analysis of Covariance (ANCOVA), the General Linear Modeling approach to compare the study groups. The HbA1c and BDI at baseline will serve as control variables. HbA1c and BDI values at baseline are the values obtained at the first visit before the start of the intervention. For that, the assumption of homogeneity of regression slope will be examined by testing the interaction effect of the independent variable and the covariate.

The following hypothesis will be tested:

$H_0: \mu_{CBT} = \mu_{control}$ versus $H_1: \mu_{CBT} \neq \mu_{control}$

Where μ_{CBT} and $\mu_{control}$ are the expected mean values of the differences in the BDI score belonging to the CBT and the control groups. The hypothesis will be tested on a 2-sided p-value with alpha ≤ 0.05 level of significance. The results will be displayed by means of the p-value, standard deviation of unadjusted values, and 95%-confidence interval. For that, the assumption of homogeneity of regression slope will be examined by testing the interaction effect of the independent variable and the covariate.

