1.2 Study Design

Prospective, randomized, parallel group, two-arm controlled trial comparing CBT vs control groups after two months of CBT intervention.

2 Analysis Populations

The study population is defined by the following key inclusion and exclusion criteria:

Key inclusion criteria

- Uncontrolled type 2 diabetes mellitus (HbA1c $\geq 6.5\%$)
- Mild mood disturbance to Moderate depression (BDI)
- 35 to 80 years of age
- Able to give informed consent and understand given information.

Key exclusion criteria

- Type I diabetes
- Psychiatric disorders other than depression or personality disorders including schizophrenia, bipolar disorder, and substance or alcohol abuse.
- Depressed patients on treatment for depression
- Suicidal patients and those diagnosed with major depressive disorder will be referred to a psychiatrist.

3 Study Centre

Al-Agouza Family Medicine Center (AFMC) is a primary healthcare center in Giza, Egypt. The AFMC patient registry (database) currently has more than 1370 family medical records. It has been maintained since 2011. It has been estimated at 11% of patients in the database are diabetics and between 48-96 new diabetic patients are seen each year.

4 Data Collection Tools

A structured questionnaire will be used to collect data from the study participants. The questionnaire includes the following:

4.1 Demographic (age, residence, gender, marital, status, education level, occupation).

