4.6 Anthropometric and Biochemical Measures

The anthropometric measurements will be performed. The weight in kg and height in cm will be measured using the UGM-200 health scale with barefoot patients, wearing light clothes, and looking at the horizon. The waist circumference in centimeters will be measured on bare skin, mid-distance between the bottom of the rib cage and the top of the iliac crest using an inelastic tape. The BMI will be calculated by dividing the weight by the height squared (BMI= weight in kg/height in cm²) (Cashin & Oot 2018).

To assess diabetes control, Fasting Plasma Glucose (FPG), 2-hour Plasma Glucose (2-h PG), and HbA1c will be performed at the AFMC clinical laboratory. Subsequently, participants will be randomized to control and treatment groups if they met our inclusion criteria.

5 Intervention

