5.1 Diabetes Education Message

All eligible patients will be offered a structured diabetes education by a trained educator as an update to ensure adequate diabetes knowledge in all trial participants. A one-session message for 30-40 minutes and covered the following:

- Pathophysiology of DM
- Early detection of diabetes symptoms
- Risk and predisposing factors
- Recognition of diabetes complications
- Self-care including diabetes-relevant behavior (e.g., nutrition, physical activity, foot care)
- Monitoring and treatment of diabetes

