5.2 Cognitive Behavioral Therapy Program

The treatment group will receive four CBT sessions twice a month for two months. The control group will be scheduled the same number of visits as a follow up for DM.

Patients in the CBT intervention group (Safren & Gonzalez 2007) received four educational sessions for 30-45 minutes once every two weeks during patients' regular follow up visits. The visits will be scheduled depending on the patient's availability. The sessions will be delivered by a trained physician. They will be on one to one basis and will be held at the AFMC outpatient clinic. The sessions included:

- Session 1: Dealing with thoughts of sadness and depression
- Session 2: Dealing with thoughts of anxiety and stress
- Session 3: Dealing with anger
- Session 4: Enhancement of coping and problem-solving skills

During the sessions, each participant worked with the healthcare provider to:

STEP 1: Identify thoughts and determine their effect on actions and feelings. Some examples include:

- a. Thoughts
 - o "What have I done to deserve this?"
 - o "This illness is some kind of punishment for bad things I have done"
 - o "I'll never find anyone who will love me."
- b. Feelings

- o "I'm a failure because I have diabetes"
- o "I am unlovable because of this illness and how I am managing it"

c. Actions

- o "There is nothing I can do to stop diabetes complications"
- o "There is no way I can manage everything I need to for diabetes"
- o Not meeting anyone, spending the weekends alone at home

STEP 2: Challenge Thoughts, analyze each thought to work out if it has been realistic or unhelpful. This can be achieved by asking questions such as:

- o What is the evidence for and against this thought?
- o Is thinking this way helping me?
- o Is there really nothing you can do?

STEP 3: Think of an alternative, balanced thought the physician will help patients change unhelpful thoughts and behaviors by teaching them some skills during they could apply daily. "I may not be able to control whether I develop complications, but I can feel in control of trying my best to keep healthy"

- o "The research shows that those who test their blood are healthier and less likely to develop long term complications"

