Patients will be encouraged to practice these changes in their daily life and discuss how they got on during the next session. This should help patients manage daily life problems and stop them from having a negative impact on their life. Patients will be encouraged to set a diabetes-specific goal in order to improve their glycemic control such as weight loss or HbA1c target values and try to achieve it at the end of the sessions.

Adherence to CBT has been determined by the number of CBT-sessions attended by participants and will be defined as follows:

- Adherent participation- 3-4 sessions of CBT
- Partially non-adherent participation- 1–2 sessions of CBT
- Non-adherent
- No participation in any session of CBT

6 Post-intervention

In the last visit three months later, all participants will be reassessed for depression using BDI and diabetes compliance using the MTA modified scale. All required labs (FPS, 2-h PG, and HbA1c) will be reperformed.

7 Treatment of Missing Values and Outliers

Appropriate methods will be employed on an individual basis for the missing values and variables normalization. The primary analyses for HbA1c and the BDI scores will be repeated after employing the last observation carried forward method (LOCF). The multiple imputation method will be employed when more than 10% but less than 40% of the values will be missing (Pedersen et al., 2017). If outliers will be apparent to bias the analysis, they will be set to missing.

8 Analysis Variables

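### The missing-baseline rule for HbA1c does not require the substitute value to precede randomisation (minor effect, one sentence to change)

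*Combined protocol and SAP*

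**What the plan says.** Section 9.2.1 defines baseline HbA1c and BDI as first-visit values from before the intervention. For HbA1c alone it adds: "If the HbA1c value at baseline is missing, the first HbA1c value obtained during the first subsequent visits will be used". The primary analysis is an ANCOVA of HbA1c change with baseline HbA1c and BDI as covariates, so the value affects both sides of the model. Baseline HbA1c is also a covariate in the BDI model of the same section, which carries no substitution rule, and in the additional HbA1c ANCOVA of Section 9.2.2.

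The visit schedule is as follows.

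- **Entry (Section 2).** Patients must have "Uncontrolled type 2 diabetes mellitus", defined as HbA1c of at least 6.5%.
- **Before randomisation (Section 4.6).** HbA1c is measured, and then: "Subsequently, participants will be randomized to control and treatment groups if they met our inclusion criteria".
- **Education (Section 5.1).** "All eligible patients will be offered a structured diabetes education by a trained educator". Its timing relative to randomisation is not stated.
- **Intervention (Section 5.2).** CBT patients "received four educational sessions for 30-45 minutes once every two weeks", and controls have the same number of visits. No HbA1c is scheduled at these visits.
- **Last visit (Section 6).** "All required labs (FPS, 2-h PG, and HbA1c) will be reperformed". This is the endpoint measurement.

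Section 7 allows for unnamed methods chosen case by case, a repeat of the primary analyses using LOCF, and this: "The multiple imputation method will be employed when more than 10% but less than 40% of the values will be missing".

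**The concern.** A baseline covariate should be fixed before treatment is assigned. Once a post-randomisation value can stand in for it, part of the treatment effect may already be in the baseline, so it is subtracted from the change score and adjusted away in the covariate. The rule sets no limit that prevents this.

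The schedule sharpens the point, because the only HbA1c planned after randomisation is the endpoint. If that value is used, the patient's change is 0 by construction and the covariate equals the outcome. An unscheduled value from an early follow-up visit would carry only a little of the effect.

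Section 7 does not displace the rule. LOCF has no earlier value to carry forward to a missing baseline. Multiple imputation starts only above 10% missing. The case-by-case provision names no method, and the specific sentence in Section 9.2.1 would govern over it.

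**Working it through.** **Inputs.** From the plan: a total of 80 (Section 10.1), two-sided 0.05, and ANCOVA on change (Section 9.2.1). The plan gives no SD, correlation, effect size, allocation ratio or share of missing baselines, so there is no figure of its own to reproduce. Assumed: n = 40 per arm, SD 1.5, correlation r between baseline and follow-up of 0.5 to 0.7, change shared by both arms c from 0 to -0.8, and true difference d = -0.60.

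**Step 1: unadjusted arithmetic.** Suppose the substitute is taken a fraction f of the way from baseline to endpoint, with linear change. A substituted patient then shows (1 - f) of the true change. With kT CBT and kC control patients substituted at random, the expected difference in mean change is

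(1 - f·kT/n)(c + d) - (1 - f·kC/n)c.

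With kT = kC = k this reduces to d(1 - f·k/n), which is pure dilution.

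- Endpoint substituted (f = 1): -0.60 × 39/40 = -0.585; × 38/40 = -0.570; × 36/40 = -0.540, for k = 1, 2 and 4.
- Two-week value (f = 1/6, taking 2 of about 12 weeks), k = 4: -0.60 × (1 - 4/240) = -0.590.

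**Step 2: the ANCOVA.** Adjustment offsets part of this, because the covariate is replaced along with the change score. The figures come from simulation: 20,000 trials per setting, nine settings of r and c, baseline BDI omitted, Monte Carlo SE about 0.002.

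| Substituted per arm | Endpoint, unadjusted | Endpoint, ANCOVA | Two-week value, ANCOVA |
|---|---|---|---|
| 0 | -0.600 | -0.598 to -0.603 | -0.598 to -0.603 |
| 1 | -0.585 | -0.586 to -0.595 | -0.594 to -0.602 |
| 2 | -0.570 | -0.576 to -0.585 | -0.594 to -0.598 |
| 4 | -0.540 | -0.557 to -0.572 | -0.590 to -0.598 |

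With the endpoint substituted, the rejection rate is 0.52 to 0.69 with one per arm and 0.51 to 0.67 with four, against 0.52 to 0.70 with none. With no true difference, type I error is 4.6% to 5.3%.

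**Step 3: when bias can run away from the null.** There are two routes, both shown for the endpoint substituted in controls only.

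- *Missingness differs by arm, with a shared change.* Step 1 with kT = 0 gives d + kC·c/n. For two controls the unadjusted shift is 2/40 × 0.3 = 0.015 at c = -0.3 and 2/40 × 0.8 = 0.040 at c = -0.8. The ANCOVA bias with no true difference is about 0.01 and 0.02 to 0.03, with type I error 4.8% to 5.2%. With the true difference of -0.60, r = 0.7 and c = -0.3, four controls give -0.622 and four CBT patients give -0.538, against -0.605 with none.
- *Missingness depends on the HbA1c level.* No shared change is needed. Take r = 0.6 and controls missing from the upper half of baseline. Their baselines lie on average 1.5 × √(2/π) = 1.197 above the mean, so regression to the mean gives an expected change of -(1 - 0.6) × 1.197 = -0.479. Setting this to 0 shifts the unadjusted difference by -0.479 × 2/40 = -0.024 with two controls and -0.479 × 4/40 = -0.048 with four. Repeated ANCOVA simulations gave -0.009 to -0.016 with two and -0.025 to -0.028 with four.

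**Step 4: the Section 7 trigger.** 10% of 80 is 8, so multiple imputation starts at 9 missing values. With the roughly 100 participants of Section 12.3 it starts at 11.

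**The case against.** The strongest reply is that the rule has a harmless reading. Nothing says that questionnaires, interview and laboratory tests all take place at one visit, so the next visit may be a further screening or laboratory visit before randomisation. An education session held before CBT might also supply an untreated value. This stands. The wording is too loose, but it does not always yield a post-randomisation value.

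The second reply is that the rule has almost nothing to act on. Eligibility requires the HbA1c result and randomisation follows it, so a missing baseline implies an enrolment deviation or a lost record. The plan reports neither. This also stands, and it is why the point is minor.

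Third, on the early-visit reading the simulated shift is barely above Monte Carlo error, and all the inputs are assumed. That is correct; visible dilution needs the endpoint itself substituted in several patients.

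A reader might go further and infer that the plan uses endpoint values as baselines, or that the rule inflates the CBT effect. The documents support neither. The endpoint is a permitted worst case and not the plain meaning of the sentence. With equal, random missingness the effect runs toward the null. Bias away from the null needs one of the conditions in Step 3, for which there is no evidence in the plan.

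What survives is that the rule as written permits a treatment-affected baseline, and no other section closes the gap.

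**Conclusion.** The point holds as a minor correction to the definition of baseline. Under the stated assumptions, endpoint substitution moves an estimate of -0.60 to about -0.59 with one patient per arm and about -0.56 with four; a two-week value leaves it almost unchanged. Type I error stays near 5% in the settings examined. The direction is dilution under equal, random missingness. It can reverse if missingness differs by arm together with a shared change, or if missingness depends on HbA1c. The exact size rests on an SD, correlation, shared change and effect that the documents do not give. That the wording lacks a pre-randomisation limit rests on the text alone. The gain from the change is a sound baseline definition and not power.

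**What to change.** Keep the first-visit definition of baseline in both paragraphs of Section 9.2.1 and replace the substitution sentence with:

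> If the first-visit HbA1c is missing, another HbA1c value obtained before randomisation (such as the eligibility laboratory value) will be used; no value obtained after randomisation may serve as baseline. If none exists, the baseline is imputed with the pooled baseline mean of both arms, whatever the missing share.

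State that this rule takes precedence over Section 7 for baseline HbA1c, and apply it wherever that value is a covariate: the primary model, the BDI model and the additional HbA1c ANCOVA of Section 9.2.2. Report by arm how many patients needed each step.

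In the same simulations, with four baselines missing at random per arm, the pooled mean gave -0.597 to -0.604 (rejection 0.51 to 0.66). It is not a cure for selective, one-sided loss. If only high-HbA1c controls are affected (r = 0.6, as in Step 3), its expected bias is about 0.6 × 1.197 × 2/40 = 0.036 with two and 0.072 with four. This is why the record look-up comes first and the counts are reported by arm. If the counts are lopsided, an ANCOVA without those patients is a useful sensitivity check.

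The cost is a few lines of SAP text and a look-up of the eligibility record for any affected patient, with no new patients or tests. Section 12.3 says the trial is already in data analysis, and Section 9 says: "An academic statistician blinded to study groups conducted the study statistical analysis". Neither shows whether results by group have been seen. The change should therefore be dated and should state whether they had been.
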